3.10.2 Recording data

Source documents shall be created and maintained by the investigation site team throughout the clinical investigation. The data reported on the eCRFs shall be derived from, and be consistent with, these source documents, and any discrepancies shall be explained in writing. The eCRFs shall be signed and dated by the principal investigator or a delegated investigator. Any change or correction to data reported on a paper CRF shall be dated, initialed and explained if necessary, and shall not obscure the original entry.

3.10.3 CARTO® data management

CARTO® (Biosense Webster, Diamond Bar, California, US) studies of all centers will be exported and anonymously sent using a secure data transfer server (eCRD platform developed by CRO Xolomon SL) and analyzed by the following core-lab: ADAS 3D Medical SL headquarters (Barcelona, Spain). Ablation settings and RF applications will be thoroughly reviewed by an expert operator of the core-lab, to ensure compliance with the LAWT protocol. Any violation of this protocol will be considered enough reason to exclude the case from further analysis.

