The CLOSE study¹⁵ analyzed the utility of AI for the reduction of AF recurrences with 91.3% of the patients free from AF/AT/atrial flutter (AFL) at 12 months follow-up. The CLOSE protocol targeted an inter-lesion distance of 6 mm and AI \geq 400 at the posterior wall and \geq 550 at the anterior wall. Nonetheless, in over 40% of patients, the target AI of 400 was not attained on the posterior wall owing to chest pain and/or intraesophageal temperature rise (IQR: 378–425 AU). The same 550 and 400 AI target values were used in a retrospective study comparing AI vs. CF-guided ablation resulting in significantly lower AT/AF recurrences on the AI arm.¹³ Such targets were chosen based on a previous study that retrospectively analyzed the ablation settings at first AF ablation of patients having redo ablation. Mean AI and mean FTI being statistically lower for reconnected segments [mean AI: 395 (350–429) vs. 422 (380–464), $p=0.002$; mean FTI: 311 (225–373) vs. 371 (260–502) gs, $p=0.003$].¹²

The left atrial wall is a thin structure with heterogeneous thickness, ranging from < 1mm to > 5 mm, with an important inter and intra-patient variability.¹⁶ This variability in wall thickness is the result of a complex array of three-dimensional muscular strands.¹⁷⁻¹⁹ A prospective study already showed that first pass PVI was limited by inability to create

transmural lesions in certain anatomical sites where left atrial wall thickness (LAWT) had been described as being higher in ex-vivo hearts.^{18,20} LAWT was an independent predictor of reconnection,²¹ dormant conduction²² and AF recurrence after 12 months follow-up,²³ and it might even be a predictor of transition from paroxysmal to chronic AF.²⁴

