The relationship between FTI and AI values, LAWT and gap formation on the ablation line after PAF ablation was already studied in two small retrospective studies that used single-point LAWT measurements. Nevertheless, the anatomical location of the measured points in the multidetector cardiac tomography (MDCT) may have not corresponded exactly to the real-time catheter position as seen with the CARTO Merge® (Biosense Webster, Diamond Bar, CA, USA) module. These studies showed that FTI/wall thickness and AI/wall thickness indexes have demonstrated to predict gaps on PVI lines.²⁵ Although this relationship might also be explained by the fact that the anatomical regions where tissue is thickest are also regions where catheter stability is more difficult to obtain. Therefore, AI is the most suitable index to look at since it also takes stability on account.

Even though many limitations have been described on MDCT atrial wall thickness measurement for previous generations of scanners, modern machines allow for sub-millimetric resolution. In fact, MDCT-derived LAWT measurements have been reliably validated on a porcine model.²⁶ 3D LAWT maps have already been generated from contrast-enhanced MDCT images,²⁷ although their integration on a 3D anatomical mapping system for clinical use has not been described yet.

Of all the determinants of lesion creation, LAWT is one key element that has been evaluated in some retrospective analysis but is not yet used as per procedure to dose the radiofrequency delivery. Adapting AI to local LAWT would be very useful in standardizing the ablation procedure with parameters fitted to each patient, enabling the development of a personalized approach that will both: i) increase efficacy by performing transmural lesions to prevent the formation of conduction gaps in the initial lesion set, and ii) increase safety by preventing excessive RF delivery on thin wall areas which can lead to complications, like cardiac perforation or atrio-esophageal fistula.

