3. METHODS

3.1 Study design

Single-arm, international, multicenter, prospective study.

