Acute PVI will be confirmed after *first pass* with the single catheter method of demonstrating entry and exit block with the ablation catheter placed sequentially in each of the PVs or trunks. There is a minimum waiting time of 10 min after isolation of each ipsilateral PV pair; additional RF applications must be performed at reconnection sites until PVI is achieved. A carina line will have to be always performed for the right pulmonary veins, since there is anatomical³⁷ and electrophysiological evidence³⁸⁻⁴⁰ for the presence of interconnections of the ipsilateral veins in up to of $\frac{2}{3}$ of the patients referred for AF ablation.⁴¹ Additional substrate ablation to create left atrial linear lesions or any extra PV-trigger ablation like CFAE is not permitted. Atrial fibrillation that persists after PVI must be terminated with electrical cardioversion. In case other substrates have to be addressed in the same procedure (i.e. right atrial arrhythmias), the additional time, vascular accesses or catheters employed after PVI will not be taken into account for the purpose of the present study.

Of note is that complete PVI will not be considered unless a second evaluating operator confirms the absence of 'visual gaps' along the ablation lines. This second operator may be any experienced professional involved in the procedure (nurse, engineer, technician, etc.) that is able to assess the presence of gaps in a reliable manner. The visual gaps will be defined as any solution of continuity between two RF lesions tagged using the VisiTag settings previously described and a 3-mm tag size. This confirmation will have to be indicated in ALL cases in the data collection sheet. Its absence will be a reason to exclude the case from the study.

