3.11 Statistical analysis

3.11.1 Sample size

The sample size calculation has been based on the assumption that the proposed ablation protocol ('LAWT') is an acceptable alternative to the CLOSE protocol¹⁵ (non-inferiority), with the advantage of less radiofrequency applied and likely lower risk for complications. A non-inferiority margin of 10% of clinical success (arrhythmia-free survival one year after the ablation procedure) will be considered to be the largest difference that is acceptable

between both protocols for LAWT to be adopted in clinical practice. Recruiting $n = 106$ participants will be required to confer 90% power to reject the inferiority null hypothesis, that is, that the lower limit of a one-sided 95% confidence interval will be above the non-inferiority limit of -0.05 , indicating no difference between the arms. A drop-out rate of 10% is estimated, and included in the sample size calculation.

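### Treated patients can be dropped after the procedure for ablation-protocol violations and no all-treated set is defined, so the single-arm comparison with CLOSE may be biased towards non-inferiority

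*Combined protocol and SAP*

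**What the plan says.** Two rules remove patients after treatment.

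- Section 3.10.3: the core-lab reviews the exported CARTO studies for compliance with the wall-thickness protocol, and "Any violation of this protocol will be considered enough reason to exclude the case from further analysis".
- Section 3.4.3: "complete PVI will not be considered unless a second evaluating operator confirms the absence of" visual gaps. The confirmation must be entered on the data collection sheet for every case, and "Its absence will be a reason to exclude the case from the study".

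Sections 3.11.1 and 3.11.2 name no analysis population and plan no analysis that retains excluded cases. Section 3.12 lists two deviations and asks that deviations be documented and reported through the eCRF; it does not mention exclusion.

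The design in section 3.1 is "Single-arm, international, multicenter, prospective study". Section 3.11.1 takes the CLOSE protocol as the reference and states the criterion in two ways: "A non-inferiority margin of 10% of clinical success" and, later, that "the lower limit of a one-sided 95% confidence interval will be above the non-inferiority limit of -0.05". The introduction gives 91.3% arrhythmia-free at 12 months for CLOSE.

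**The concern.** In a randomised non-inferiority trial, a per-protocol set is often used because it can be the more cautious choice. That argument needs a concurrent arm subject to the same exclusions. Here the exclusions act on the tested arm alone, and the reference is a fixed external figure. Any link between exclusion and outcome passes straight into the estimated success rate.

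The protocol's own background makes such a link plausible. The introduction says that "the anatomical regions where tissue is thickest are also regions where catheter stability is more difficult to obtain", that "LAWT was an independent predictor of reconnection" and of recurrence at 12 months, and that gaps in the lesion line cause recurrence. Anatomy that makes the protocol hard to follow may therefore also make recurrence more likely, and one of the two triggers is itself a check for gaps.

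At stake is what the primary result describes: all patients treated with this strategy, or only those in whom it was carried out as specified. The plan sets no limit on exclusions and does not require the outcomes of excluded cases to be reported, so a reader could not tell a harmless situation from a misleading one. It is also unclear whether complications in excluded cases stay in the safety results: section 3.13 says all are documented, but section 3.10.3 makes no exception for safety.

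**Working it through.** The plan gives no figure for exclusions, so there is nothing of its own to reproduce. The calculation shows how large the effect could be.

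**Inputs from the documents**
- Reference success 91.3% (introduction).
- Margin 10 points, so the non-inferiority boundary is 91.3 − 10 = 81.3%. With the −0.05 limit it is 91.3 − 5 = 86.3%.
- One-sided 5% level (3.11.1).
- 106 recruited with 10% drop-out: 106 × 0.90 = 95.4, taken as 95 with follow-up.

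**Assumptions, not in the documents**
- Share of treated cases excluded, e: 2, 5, 10 or 20%.
- Recurrence ratio, excluded to retained, RR: 1.5 to 3.
- Exact binomial test against the fixed reference.

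**Formula.** If recurrence among all treated patients is r, recurrence among retained patients is

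r0 = r / [(1 − e) + e × RR].

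The number analysed is 95(1 − e), rounded: 93, 90, 86 and 76. For each n, find the smallest success count with exact one-sided p ≤ 0.05 at the boundary, then the probability of reaching it when true all-treated success lies on the boundary but the retained success rate is 1 − r0.

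**Worked case.** 10-point margin, e = 10%, RR = 3: r = 0.187 and r0 = 0.187 / (0.9 + 0.3) = 0.156, so retained success is 84.4%. With n = 86 the count needed is 77. The probability of reaching it is 12.0%, against 2.8% if exclusion is unrelated to outcome.

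**False non-inferiority, 10-point margin (true success 81.3%)**

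| Excluded | n | Successes needed | RR = 1 | RR = 1.5 | RR = 2 | RR = 3 |
|---|---|---|---|---|---|---|
| 2% | 93 | 83 | 2.8% | 3.1% | 3.4% | 4.0% |
| 5% | 90 | 80 | 3.8% | 4.7% | 5.8% | 8.4% |
| 10% | 86 | 77 | 2.8% | 4.4% | 6.5% | 12.0% |
| 20% | 76 | 68 | 4.0% | 8.3% | 14.4% | 29.9% |

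**False non-inferiority, −0.05 limit (true success 86.3%)**

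| Excluded | n | Successes needed | RR = 1 | RR = 1.5 | RR = 2 | RR = 3 |
|---|---|---|---|---|---|---|
| 2% | 93 | 86 | 4.9% | 5.3% | 5.7% | 6.5% |
| 5% | 90 | 84 | 2.9% | 3.5% | 4.2% | 5.8% |
| 10% | 86 | 80 | 4.1% | 5.7% | 7.7% | 12.7% |
| 20% | 76 | 71 | 4.2% | 7.6% | 12.2% | 23.4% |

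The exact test is discrete, so each row should be compared with its own RR = 1 column and not with another row. With nobody excluded (n = 95) the rates are 4.4% (84 successes needed) and 4.2% (88 needed).

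**Bias in the estimate.** If true all-treated success is 91.3%, the analysed rate is too high by 0.087 − r0, with r = 0.087. For RR 1.5 to 3 this is 0.1–0.3 points with 2% excluded, 0.2–0.8 with 5%, 0.4–1.5 with 10% and 0.8–2.5 with 20%.

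**Other direction.** If excluded cases recur half as often (RR = 0.5), false non-inferiority with the 10-point margin falls to 1.5–2.9% across the four exclusion rates.

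**The case against.** The best counter-argument is that neither the direction nor the size of the bias is established.

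- The form in Appendix 2 asks whether the second operator evaluated the case for gaps, not whether gaps were found. A missing confirmation may be only a skipped or unrecorded check, unrelated to outcome.
- Section 3.4.3 requires a missed Ablation Index target to be re-treated, asks for the esophagus to be avoided only where possible, and continues ablation until isolation. Some potential violations are corrected on the table or are not violations at all.
- Extra-PV ablation, a listed deviation, means more ablation than planned. Excluding such cases could lower observed success.
- Section 3.12 treats deviations as events to document, and the wording in 3.10.3 can be read as permissive.
- CARTO data reach the core-lab anonymised, and nothing says it sees outcomes.
- The documents do not give the analysis set used in CLOSE.

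Most of this stands as a limit on size and direction: the effect is small with few exclusions, and clerical exclusions need not bias. It does not remove the problem. Section 3.12 does not cancel 3.10.3, so the two are unreconciled. Anonymised transfer is not a rule that compliance be judged without knowledge of outcome. Whatever CLOSE did, this plan's rules act only on this study's patients.

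**Conclusion.** The concern holds. As written, the plan allows treated patients to leave the primary analysis for reasons that may be related to outcome, and it defines no all-treated set against which to check the result. In a single-arm comparison with an external rate, that can move the conclusion towards non-inferiority.

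The size depends on two quantities the documents do not give. With 2% excluded, the false non-inferiority rate rises by at most 1.6 points over the same-n value under either limit (4.9% to 6.5% at the −0.05 limit). With 10% excluded and recurrence 1.5 to 3 times higher in excluded cases, it is 4.4–12.0% for the 10-point margin and 5.7–12.7% for the −0.05 limit. With 20% excluded it is 8.3–29.9% and 7.6–23.4%. These are illustrations under a fixed 91.3% reference and an exact one-sided 5% test. The bias vanishes if excluded patients do as well as the rest, and reverses if they do better.

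The point should be settled before analysis because it decides who is counted in the primary endpoint. If excluded patients are not followed, the loss may not be recoverable.

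**What to change.** - In 3.11.2, define the primary and safety analysis set as all consented patients in whom the ablation-by-LAW procedure was started.
- In 3.4.3 and 3.10.3, replace exclusion with recording as a protocol deviation, and align both with 3.12.
- Keep these patients in the scheduled follow-up.
- Require the core-lab to record compliance without sight of outcome.
- Report the compliant set as a labelled sensitivity analysis, with the number, reasons and outcomes of non-compliant cases.
- In 3.11.1, state what the 10% drop-out allowance covers.

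The cost is wording changes in these sections and continued scheduled visits for patients who would otherwise be dropped. The headline success rate may be slightly lower. The estimate in compliant cases is still reported.

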3.10.4 Review of data

The clinical investigation will be monitored by reviewing the eCRF submitted by the investigators. The following activities will occur:

- All eCRFs will be reviewed for completeness and accuracy upon receipt by the principal investigator.
- The investigator (co-investigator) and/or delegate will be contacted by the principal investigator regarding any missing or unclear data.

3.11 Statistical analysis

3.11.1 Sample size

The sample size calculation has been based on the assumption that the proposed ablation protocol ('LAWT') is an acceptable alternative to the CLOSE protocol¹⁵ (non-inferiority), with the advantage of less radiofrequency applied and likely lower risk for complications. A non-inferiority margin of 10% of clinical success (arrhythmia-free survival one year after the ablation procedure) will be considered to be the largest difference that is acceptable

between both protocols for LAWT to be adopted in clinical practice. Recruiting $n = 106$ participants will be required to confer 90% power to reject the inferiority null hypothesis, that is, that the lower limit of a one-sided 95% confidence interval will be above the non-inferiority limit of -0.05 , indicating no difference between the arms. A drop-out rate of 10% is estimated, and included in the sample size calculation.

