3.11.2 Statistical methods

All applicable statistical tests will be 2-sided and will be performed using a 5% significance level. Continuous variables will be reported as mean \pm standard deviation, or median (range or interquartile range if data are skewed) if not normally distributed; these variables will be compared using Student's t-test if normally distributed or Mann-Whitney U test if not normally distributed. Categorical variables will be expressed as total number (percentage) and will be compared by chi-squared test. For the primary endpoint, survival free from atrial arrhythmia, we will use the Kaplan-Meier survival analysis. A multivariable Cox proportional hazards model will be performed to investigate the effects of baseline characteristics in predicting ablation results, an adjustment will also be done by recruiting center. A receiver operating curve analysis will be performed to determine optimal cutoff LAWT values for predicting AF recurrence after ablation. All efforts will be done to limit missing data on outcome. Nevertheless, missing data will be reported on the final manuscript and, as much as possible, the reasons why data are missing will be documented. If missing, a simple imputation method will be applied and reported.

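### The lower limit that decides non-inferiority has no stated interval method, and two ordinary Kaplan-Meier limits would exceed the 5% error rate if 91.3% is the fixed reference

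*Combined protocol and SAP*

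**What the plan says.** The design is given in section 3.1 as "Single-arm, international, multicenter, prospective study". Section 3.11.1 sets out to show that the new protocol "is an acceptable alternative to the CLOSE protocol" and makes the conclusion depend on whether "the lower limit of a one-sided 95% confidence interval will be above the non-inferiority limit". It gives the margin twice, with different values: "A non-inferiority margin of 10% of clinical success" and "above the non-inferiority limit of -0.05". It states 106 participants, 90% power and 10% drop-out already allowed for. It does not state the reference success rate. The only CLOSE figure in the document is in the Introduction: "91.3% of the patients free from AF/AT/atrial flutter (AFL) at 12 months follow-up".

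Section 3.11.2 says: "For the primary endpoint, survival free from atrial arrhythmia, we will use the Kaplan-Meier survival analysis". It does not say that the deciding limit comes from that analysis, and nothing in the document names a variance estimator, a transformation, or a score or exact interval. The same section adds a general rule: "All applicable statistical tests will be 2-sided and will be performed using a 5% significance level".

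**The concern.** With one arm, a single confidence limit carries the whole primary conclusion. That limit concerns a proportion expected near 0.9, from roughly 95 to 106 patients, so only about ten recurrences are expected. In this region the common Kaplan-Meier limits differ. The plain (Wald-type) and log-transformed Greenwood lower limits sit too high, while the complementary log-log limit does not do so systematically. Any of them would satisfy the text.

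Two things are at stake. The error rate implied by a one-sided 95% limit may not be the one delivered. And if the choice is made once the number of recurrences is known, the same data can support either conclusion.

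**Working it through.** **Inputs.** Reference 0.913 (Introduction), treated as a fixed constant by assumption. Margin 0.10 or 0.05 (section 3.11.1), so the null success rate is 0.913 - 0.10 = 0.813 or 0.913 - 0.05 = 0.863. One-sided 5%, z = 1.645. Enrolled 106; with 10% drop-out, 106 × 0.9 = 95.4, so about 95 complete.

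**Step 1: the plan's own power.** The one-sample score formula is Φ[(δ√n - z√(p0(1-p0))) / √(p1(1-p1))]. With δ = 0.10, p0 = 0.813, p1 = 0.913 and n = 95, this is (0.975 - 0.641) / 0.282 = 1.18, giving 88.2%. At n = 106 it is 91.6%. The stated 90% is therefore consistent with a 10-point margin and a fixed 91.3%. With the 5-point margin the formula gives 43% at n = 106.

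**Step 2: one data set, several limits.** Take 83 successes of 95, S = 0.8737. With no censoring, the Greenwood standard error is √(0.8737 × 0.1263 / 95) = 0.0341.

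- Plain: S - z·se = 0.8737 - 0.0561 = 0.818
- Log: S·exp(-z·se/S) = 0.8737 × exp(-0.0642) = 0.819
- Log-log: S^exp(z·se/(S·|ln S|)) = 0.8737^1.608 = 0.805
- Wilson: 0.807
- Exact: 0.803

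Against 0.813, plain and log pass; the other three fail.

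**Step 3: exact binomial error and power, 95 complete.** Power is at a true success rate of 91.3%.

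| Null rate | Limit | Successes needed | False non-inferiority | Power |
|---|---|---|---|---|
| 0.813 | plain, log | 83 | 7.8% | 93.2% |
| 0.813 | log-log, Wilson, exact | 84 | 4.4% | 87.8% |
| 0.863 | plain, log | 87 | 8.3% | 55.4% |
| 0.863 | log-log, Wilson, exact | 88 | 4.2% | 40.9% |

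**Step 4: with censoring.** Kaplan-Meier with Greenwood variance was simulated for 106 enrolled, with recurrences between months 3 and 12 and uniform, non-informative drop-out times (200,000 trials per row).

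| Null rate | Drop-out | Plain | Log | Log-log |
|---|---|---|---|---|
| 0.813 | 0% | 8.9% | 8.9% | 5.2% |
| 0.813 | 5% | 7.0% | 7.4% | 3.9% |
| 0.813 | 10% | 7.4% | 8.0% | 4.1% |
| 0.863 | 0% | 7.2% | 7.2% | 3.7% |
| 0.863 | 5% | 8.7% | 8.9% | 4.3% |
| 0.863 | 10% | 8.1% | 8.8% | 3.6% |

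With 10% drop-out, simulated power against 0.813 is about 88% for log-log and 93-94% for plain and log.

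**Step 5: dependence on the number analysed.** The count of successes is discrete, so the error moves with n. For every complete n from 85 to 106, across both null rates, plain and log range from about 5.5% to 11.6% and are above 5% throughout. Log-log ranges from about 2.4% to 5.3%.

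**The case against.** The strongest objection is that the rule analysed here is not quite the rule written. Section 3.11.1 compares a limit with -0.05 and speaks of a difference between arms. It does not describe a one-sample limit set against 0.813 or 0.863, and section 3.11.2 does not link Kaplan-Meier to that limit. This stands, and the figures are conditional on that reading. It is nevertheless the natural one for a single-arm study, and no other method for the limit is offered.

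Second, the unreconciled margin and the missing reference rate are larger gaps than the choice of interval. This also stands: a sentence that named only the transformation would leave the decision rule undefined. The converse holds too. Settling the margin would not settle the interval, because plain and log exceed 5% under both margins. Applying the general two-sided 5% rule would change the limit but still leave its method unnamed.

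Third, drop-outs may not be censored as simulated. Section 3.11.2 allows a simple imputation, and sections 3.4.3 and 3.10.3 exclude some cases, so the analysed number is uncertain. That widens the range but does not remove the excess. If everyone had an outcome, plain and log would give 8.9% or 7.2% at 106.

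Fourth, log-log is not the only sound choice, nor always below 5%. Logit and Wilson behave similarly, and Wilson reaches 5.8% at 100 complete against 0.863.

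A reader might infer that the plan has adopted a faulty interval, or that its error rate is 7-9%. The documents support neither, because no interval is named.

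**Conclusion.** The concern holds as a gap in specification with a measurable consequence. If the limit is that of the 12-month Kaplan-Meier estimate against a fixed 91.3%, two ordinary choices that satisfy the text give about 7-9% false non-inferiority in the planned case, against about 4% for log-log. At 95 complete and a 10-point margin, the choice decides the result at 83 successes.

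The size rests on four assumptions: 91.3% is the intended reference, its sampling error is ignored, drop-out is non-informative, and the number analysed is near plan. The 7-9% should be quoted as approximate. The direction is firmer, since the excess appears at every complete n from 85 to 106 and under both margins. It would be too strong to say that log-log guarantees 5%; it can slightly exceed it, at up to about 5.3%.

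**What to change.** In section 3.11.2, state that non-inferiority is decided on the one-sided 95% lower limit of the 12-month Kaplan-Meier estimate with the complementary log-log transformation. State that this limit is compared with an explicit reference rate minus a single margin, after the 10% and -0.05 figures have been reconciled. Name a Wilson or exact binomial limit as sensitivity analysis, and say that the general two-sided rule does not apply to this decision.

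In section 3.11.1, restate the power for that limit at 95 evaluable and true success 91.3%: about 88% with a 10-point margin, slightly below the stated 90%, or about 41% if the -0.05 limit is the one kept.

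The cost is a short addition to the text and a less favourable power statement (88% rather than the 93% that the plain limit would show). With the 10-point margin, no extra enrolment is needed if about 88% is accepted. Holding 90% would take about 101 evaluable patients by the score or exact calculation, or 101 / 0.9 = 112.2, so 113 enrolled.

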2. HYPOTHESIS AND OBJECTIVES

2.1 Research hypothesis

Personalized AF ablation using the ‘*ablation-by-LAW*’ protocol that uses point-by-point adapted AI values according to the local MDCT-derived LAW_T, is feasible, safe and at least as effective as the current AF ablation standards.

Ablation-by-LAW involves the use of tailored point-by-point AI values according to the local MDCT-derived LAW_T, the use of a single-catheter strategy, and the integration of a MDCT-derived ‘fingerprinted’ esophagus image to modify the ablation lines aiming to avoid too close RF applications, while performing the procedures using general anesthesia and a high-rate, low-volume ventilation protocol. The following diagram constitutes a general overview of the protocol:

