2.2 Study objectives

2.2.1 Primary objective

To determine if the proposed *ablation-by-LAW* protocol is non-inferior in terms of long-term clinical outcomes when compared to other AF ablation protocols using higher AI targets, not adapted to the LAWT.

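### Section 3.11.1 gives two incompatible non-inferiority limits (10% and -0.05) and no reference or expected rate; if the true rate is 91.3%, n = 106 gives about 41–55% power against -0.05, not 90%

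*Combined protocol and SAP*

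**What the plan says.** Section 3.11.1 names the CLOSE protocol as comparator and sets "A non-inferiority margin of 10% of clinical success", which "will be considered to be the largest difference that is acceptable" between the two protocols. The next sentence says 106 participants are needed "to confer 90% power to reject the inferiority null hypothesis", and defines that rejection as the "lower limit of a one-sided 95% confidence interval will be above the non-inferiority limit of -0.05", "indicating no difference between the arms". On attrition: "A drop-out rate of 10% is estimated, and included in the sample size calculation".

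The section gives no reference rate, no expected rate under the study protocol and no method for the confidence limit. The only 12-month success rate in the document is 91.3% for CLOSE, reported as background in the Introduction. Section 3.1 describes a single-arm study. Section 3.11.2 makes all applicable tests two-sided at 5% and names Kaplan-Meier analysis for the primary endpoint, without a decision rule. The claim sought is non-inferiority only: the hypothesis (2.1) is "at least as effective as the current AF ablation standards", and the primary objective (2.2.1) is to be "non-inferior in terms of long-term clinical outcomes when compared to other AF ablation protocols using higher AI targets".

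**The concern.** A margin of 10 points and a limit of -0.05 are two different success criteria for the same endpoint, stated in consecutive sentences. The first is described as the clinically acceptable loss; the second is the one attached to the sample size and power. A reader cannot tell which result would count as success, and the choice could be made after the outcomes are known.

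This is the trial's only confirmatory claim, so two things are at stake. The primary conclusion may turn on which sentence is followed, and the stated 90% power may be far from the truth for the limit it is attached to. The reference in the same sentence to arms that a single-arm study does not have leaves the comparison itself undefined.

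**Working it through.** **Inputs.** From 3.11.1: n = 106, power 90%, one-sided 5%, drop-out 10% included, limits 10 points and -0.05. Evaluable: 106 × 0.9 = 95.4, taken as 95. Assumption, because 3.11.1 gives no rate: the reference is fixed at CLOSE's 91.3% (Introduction). The bars are then 91.3 − 10 = 81.3% and 91.3 − 5 = 86.3%.

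**Can 106 be reproduced?** Two standard one-sample formulas, with z(0.95) = 1.645, z(0.90) = 1.282, true rate p1, bar p0 and d = p1 − p0:

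- Alternative variance: n = p1(1 − p1) × [(1.645 + 1.282)/d]²
- Score: n = [1.645√(p0(1 − p0)) + 1.282√(p1(1 − p1))]² / d²

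Enrolled = evaluable / 0.9, rounded up.

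| Case | Evaluable (alt. variance / score) | Enrolled |
|---|---|---|
| p1 = 0.913, p0 = 0.813 | 69 / 101 | 77 / 113 |
| p1 = 0.913, p0 = 0.863 | 273 / 344 | 304 / 383 |
| p1 = 0.95, p0 = 0.863 | 54 / 95 | 60 / 106 |

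With no true difference from 91.3%, the 10-point margin brackets 106 and -0.05 needs roughly three times as many. Exactly 106 arises only from inputs that 3.11.1 does not state:

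- Limit -0.05, true rate 95%, score formula: 94.3, so 95 evaluable; 95/0.9 = 105.6, so 106.
- Margin 10 points, true and reference rate both 90%, one-sided 0.025, alternative variance: 0.90 × 0.10 × [(1.960 + 1.282)/0.10]² = 94.6, so 95 evaluable and 106 enrolled.

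One route uses each limit, so the sample size does not show which was meant.

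**Cut-offs and power with 95 evaluable, one-sided 5%.** The cut-off is the smallest number of successes whose lower limit exceeds the bar. Power is the binomial probability of reaching it.

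| Bar | Bound | Cut-off (lower limit) | Type I error | Power at 91.3% |
|---|---|---|---|---|
| 81.3% | Exact | 84 (81.6%) | 4.4% | 87.8% |
| 81.3% | Wald | 83 (81.8%) | 7.8% | 93.2% |
| 86.3% | Exact | 88 (86.6%) | 4.2% | 40.9% |
| 86.3% | Wald | 87 (86.9%) | 8.3% | 55.4% |

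Log(−log) and score bounds give the same cut-offs as the exact bound at n = 95. If all 106 are evaluable, power against -0.05 at 91.3% is 42.0% (exact) or 55.7% (Wald).

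**Sensitivity of power against -0.05 to the true rate (95 evaluable).**

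| True rate | Exact | Wald |
|---|---|---|
| 90% | 26% | 38% |
| 91.3% | 41% | 55% |
| 93% | 65% | 78% |
| 94% | 79% | 88% |
| 95% | 90% | 95% |

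The true rate needed for 90% power is 95.0% (exact) or 94.2% (Wald).

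**Where the two limits disagree.** Under the exact bound, 84–87 successes pass at 10 points and fail at -0.05; under Wald, 83–86 do. The expected count at 91.3% is 95 × 0.913 = 86.7. The probability of landing in the band is 46.9% (exact) or 37.8% (Wald).

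**The case against.** The strongest reply is that -0.05 is a drafting slip. The 10-point margin, a 90% rate for both protocols and a one-sided 0.025 level (the two-sided 5% of 3.11.2) give exactly 106 without assuming any benefit over CLOSE, which fits a non-inferiority aim. If so, 41–55% describes a limit that was never used for sizing. The route to 106 under -0.05 is also formula-dependent: the alternative-variance version gives 60, not 106.

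This is plausible but does not settle the matter. The 90% rate appears nowhere as an input, 3.11.1 states one-sided 95%, and this route is formula-dependent too: with the score formula the same inputs give 137 evaluable. A slip in the success criterion still has to be corrected.

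Other points stand as qualifications:

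- The power figure is conditional on a fixed reference and a true rate of 91.3%. The contradiction between the limits needs neither.
- The 91.3% is background, not a declared sizing input; 2.2.1 speaks of other protocols in the plural; and treating the rate as fixed ignores CLOSE's own sampling error. It is used here because CLOSE is the comparator named in 3.11.1 and this is its only rate in the document.
- The success counts assume 95 complete binary outcomes. Kaplan-Meier estimation, imputation, and the exclusions allowed in 3.4.3 and 3.10.3 would shift them, so the bands are illustrative.
- If one-sided 0.025 was intended, exact power for the 10-point margin with 95 evaluable falls to about 80% (rate 91.3%) or 76% (rate 90%).

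**Conclusion.** The concern holds and must be fixed. Section 3.11.1 contains two non-inferiority limits that cannot both apply, and the document offers no means of choosing between them. With a fixed 91.3% reference, one-sided 5% and 95 evaluable patients, the choice reverses the primary conclusion over a four-count range that includes, or lies next to, the most likely results. The 90% power claim is unsupported for the limit it is attached to unless the true rate is about 94–95%, for which the plan gives no basis. It is close to right for the 10-point margin. Confidence is high on the contradiction and the missing inputs; the power figures are as good as the 91.3% assumption.

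**What to change.** Before outcome data are reviewed, the sponsor should amend 3.11.1 as follows.

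1. Confirm one margin and delete the other. The 10-point margin is the one the text justifies and, with no true difference, the one compatible with 106. The choice is the sponsor's.
2. Replace "indicating no difference between the arms" with a decision rule, for example: *Non-inferiority is concluded if the lower limit of the one-sided 95% confidence interval for 12-month arrhythmia-free survival exceeds 91.3% minus the margin* (81.3% for 10 points, 86.3% for 5).
3. State the reference rate and that it is treated as fixed, the assumed true rate, and the interval method. A plain Wald bound has about 8% type I error here, so a log(−log) or exact-type bound is preferable.
4. Restate power: about 88% for 10 points at 91.3%. If -0.05 is confirmed, state about 41% at 91.3%, or state and justify a higher assumed rate (about 95% for 90% power).
5. Add a clause to 3.11.2 that the one-sided 5% bound in 3.11.1 governs the primary test. If the sizing in fact used 0.025, say so and restate power accordingly.

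Cost: wording only if 10 points stands at one-sided 5%, or if -0.05 stands with a justified rate near 95%. If -0.05 is meant, the true rate is 91.3% and 90% power is kept, about 304–383 would have to be enrolled.
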